	- Intake of proton pump inhibitors (F Pis) on a regular basis - Intake of antibiotics within the last 3 months before inclusion
	- Intake of pro or prebiotics
	- Chronical diseases of the gastrointestinal tract, history of gastrointestinal surgery with
	major changes to the gastrointestinal tract - Substance abuse, alcohol abuse.
	- Substance abuse, accord abuse Inability to follow procedures due to psychological disorders, dementia or insufficient
	knowledge of project language (German).
	Over a period of 7 weeks, volunteers will ingest the natural sweetener xylitol or erythritol
Measurements and	(or no additional sweetener). Once before and after these 7 weeks we will carry out an
procedures:	oral glucose tolerance test, examine faeces and urine (gut microbiota and metabolomics)
	and take blood samples to analyse lipid profile and liver enzymes. Volunteers will fill in
	a food diary and a questionnaire for gastrointestinal symptoms. The whole study will take
	approximately 8 weeks.
Otrode Due doot /	Randomization to the three study arms will be done by a computer based randomization
Study Product /	(excel). The control group will not receive any sweetener.
Intervention:	The two intervention groups will receive either xylitol or erythritol as follows:
	1st week = run-in (adaption week)
	- 2 days 1 *portion per day (1-0-0)
	- 3 days 2 portions per day (1-1-0)
	- 2 days 3 portions /day (1-1-1)
	2nd to 7th week: Over four weeks the volunteers will ingest 3 portions/day.
	*1 portion xylitol = 8g, 1 portion erythritol = 12g
Control Intervention	We will compare
	a) Baseline findings to post treatment findings. In this way each volunteer will serve as
	his/her own control.
	b) A control group will show whether findings are stable within a participant over 7 weeks.
Number of	In total will enrol 60 volunteers, of which 20 will be controls, 20 will be treated with xylitol
Participants with	and 20 erythritol. This is a pilot trial and a power analysis is not possible. However, we
Rationale:	assume that a relevant difference between the treatments should be observed in 20
-	subjects in each group.
Study Duration:	We plan to carry out this trial within approximately 1 year, starting in August 2016 till
	October 2018, depending on recruitment.
Study Schedule:	Month Year of First-Participant-In (planned): 1st August, 2016
Investigates/a	Month Year of Last-Participant-Out (planned): 1st October, 2018
Investigator(s):	[name] [name]

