2. BACKGROUND AND RATIONALE

2.1 Background and Rationale

Obesity has increased significantly worldwide¹. In morbid obesity virtually all patients suffer from metabolic syndrome with non-alcoholic fatty liver disease, dyslipidaemia and impaired glycaemic control. Sugar consumption - in the form of sucrose or high-fructose corn syrup (HFCS) - has partly contributed to the dramatic rise in obesity, metabolic syndrome and diabetes^{2,3}. Research on the effects of dietary sugars on health has recently focused on fructose, given the striking parallel increases in obesity and in fructose intake over the past decades^{4,5}. Fructose intake in diets mostly originates from sucrose (containing 50% fructose and 50% glucose) and soft drinks containing high-fructose corn syrup (HFCS)⁶. Patients with non-alcoholic fatty liver disease (NAFLD) consume double the amount of calories of HFCS from beverages than healthy patients⁷. The increasing evidence of the detrimental role of sucrose and fructose justifies a reduction in intake and substitution of sugar by alternative dietary sweeteners. However, alternatives are not so easy to find.

Various nutrients have shown to influence gut microbiota positively or negatively. Lately, a study was published demonstrating that consumption of commonly used artificial sweeteners drive the

development of glucose intolerance through induction of compositional and functional alterations to the intestinal microbiota⁸.

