6. STUDY POPULATION

6.1 Eligibility criteria

Participants fulfilling all of the following inclusion criteria are eligible for the study:

- Obese volunteers (BMI > 30kg/m2) aged 18- max. 55 years
- Otherwise healthy.
- Informed Consent as documented by signature (Appendix Informed Consent Form)

The presence of any one of the following exclusion criteria will lead to exclusion of the participant:

- Known cardiovascular disease (coronary heart disease, cardiopathy, arrhythmia, pace-maker)
- Diabetes mellitus treated by oral antidiabetics or insulin
- Arterial hypertension with antihypertensive treatment
- Dyslipidaemia with statin therapy
- Known chronic hepatic disease (NASH, hepatitis). NAFLD is no exclusion criterion
- Known renal disease: kidnev failure
- Pregnancy: although no contraindication for polyol intake, pregnancy might influence metabolic state and vascular function
- Women who are pregnant, Intention to become pregnant during the course of the study,
- Lack of safe contraception, defined as: Female participants of childbearing potential, not using
 and not willing to continue using a medically reliable method of contraception for the entire study
 duration, such as oral, injectable, or implantable contraceptives, or intrauterine contraceptive

- devices, or who are not using any other method considered sufficiently reliable by the investigator in individual cases
- Chronical diseases of the gastrointestinal tract (also irritable bowel disease, food intolerance), history of gastrointestinal surgery with major changes to the gastrointestinal tract (removal of stomach, larger portions of the small bowel/colon, any bypass).
- Intake of prebiotics (such as inulin, oligofructose) on a regular basis
- Intake of probiotics (e.g. capsules with live bacteria or yeasts) on a regular basis
- Intake of pro/prebiotic food on a regular basis (e.g. Activia, Actimel, Aktifit, Yacult etc). Intake of common yoghurt is allowed, but limited to 1 serving/day
- Substance abuse, alcohol abuse
- Inability to follow procedures due to psychological disorders, dementia or insufficient
- Knowledge of project language (German).
- Participation in another study with investigational drug within the 30 days preceding and during the present study.

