7.2.2 Control Intervention

Participants assigned to the control-group get no sweetener, but will also go through all assessments.

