8.3.2 Second Visit = 1. Metabolic Visit

The **second visit (1. metabolic visit)** at our outpatient clinic will take about 2.5 hours. We will carry out an oral glucose tolerance test and take blood, and urine samples. If possible, the participant will bring the first faecal sample to this visit. Again, the participant has to arrive on an empty stomach (not allowed to eat or drink 10 hours prior to this appointment except for tap water or unsweetened herbal tea without milk). Even chewing gum must be avoided, as they might contain sugar. In addition 2 days prior to the test the participant has to refrain from heavy physical activity and needs to have carbohydrates as part of her/his meals.

- The candidate will be assigned randomly to one of the three groups (intake of xylitol, or erythritol or control group).
- The participant needs to bring his/her study folder along, including the food diary which he/she should have kept over the course of 1 week.
- If possible, the participant will bring along the first faecal sample
- We will take a first blood sample to measure blood sugar, insulin, C-peptide (for the oral glucose tolerance test). In addition we will measure biomarkers of inflammatory response (IL-6, TNF- α, sTNFR1, sTNFR2) and intestinal permeability (zonulin and LPS).
- The participant will receive 75 g of glucose (grape sugar) plus 3g 3-O-Methyl-D-glucose dissolved in 300mL tap water which he/she will have to drink over a period of 5-10min. ("oral glucose tolerance test")
- After 30, 60, 90 and 120min we will again take blood samples for measurement of blood sugar, insulin, C-peptide and 3-OMG. In total we will take a maximum of 30mL blood (corresponding to 3 tablespoons).
- During this appointment we will fill in the questionnaire for gastrointestinal symptoms together with the participant.
- At the end of the visit, the participant will receive the portioned sweeteners (if assigned to one of the polyol groups) and the kit for the second faecal sample.

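### Regular users of xylitol or erythritol are not excluded and no arm is told to avoid non-study sources, so habitual exposure can dilute both planned comparisons

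*Protocol*

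**What the plan says.** **Eligibility.** Protocol Section 6.1 excludes "Intake of prebiotics (such as inulin, oligofructose) on a regular basis" and "Intake of probiotics (e.g. capsules with live bacteria or yeasts) on a regular basis". It also excludes regular use of pro- or prebiotic foods, with brand examples, and adds that "Intake of common yoghurt is allowed, but limited to 1 serving/day". Neither this list nor the shorter one in the synopsis mentions xylitol, erythritol, other polyols or artificial sweeteners.

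**Control arm.** Section 7.2.2: "Participants assigned to the control-group get no sweetener, but will also go through all assessments". Section 7.1.2 says this arm receives no supplement. The synopsis (Measurements and procedures) has volunteers take one of the two polyols "or no additional sweetener", and the German summary likewise has controls take nothing extra.

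**Restrictions during the trial.** Section 7.6 (preventive measures) deals only with antibiotics. Sections 8.3.2 and 8.3.5 include a gum rule, "Even chewing gum must be avoided, as they might contain sugar", which belongs to the fast before the glucose tolerance test. Sections 7.3 and 7.4 govern intake of the supplied sticks.

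**Diet recording.** Section 8.2.3 plans a nutrition-habits questionnaire before inclusion and a diary in weeks 3 and 7. Section 8.3.1 adds a 7-day diary before intake starts. Section 5.1 describes a diary over the whole period that also captures sweetener intake. The stated purpose in Sections 4.3, 5.2 and 8.2.3 is to assess sugar consumption.

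**Comparisons.** Section 10.4.1 plans before-after comparisons within the sweetener groups, then post-treatment values of each sweetener group against a control group described as without treatment.

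**The concern.** The two test substances are ordinary food additives (Section 1.8), described as natural sugar replacers (Section 2.1) and, in the German summary, as used in dental care. An eligible volunteer could already be taking one of them and could continue in any arm. Section 6.1 goes as far as servings of yoghurt to protect the microbiota outcome, yet is silent on prior exposure to the interventions themselves.

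At stake are the glycaemic primary outcome and the microbiota outcome. Habitual exposure pulls both planned comparisons toward no difference, and the findings are meant to inform larger studies (Sections 10.1 and 10.2).

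**Working it through.** The protocol has no figure to reproduce on this point. The check is textual, followed by simple algebra on the direction of the effect.

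**Step 1: is habitual use excluded or barred anywhere?**

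| Place in Protocol | What it covers | Covers habitual polyol use? |
|---|---|---|
| Synopsis and 6.1, exclusions | pre- and probiotics; 6.1 adds the yoghurt limit | No |
| Synopsis and German summary, control arm | nothing additional taken | Bars adding, not continuing |
| 7.1.2, 7.2.2 | what controls are given | No |
| 7.3, 7.4 | schedule and compliance for study sticks | No |
| 7.6 | antibiotics | No |
| 8.3.2, 8.3.5 | gum before the glucose test, because of sugar | No |
| 4.3, 5.1, 5.2, 8.2.3, 8.3.1 | recording of diet, aimed at sugar | May reveal it; no exclusion or analysis rule follows |

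**Step 2: which comparison is affected, and how?**

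Let Δ be the effect of the study sweetener on an outcome in a person not previously exposed. Assume for simplicity that a habitual user already shows the full effect, and that the study dose adds nothing further.

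- *Before-after, sweetener arm.* If a share f of the arm are habitual users, they change by 0 and the rest by Δ. Mean change = (1 − f)Δ.
- *Post-treatment, sweetener versus control.* Habitual users in the sweetener arm are still exposed at V3, so the sweetener mean is shifted by the full Δ whatever f is. If a share c of controls are habitual users, the control mean is shifted by cΔ. Contrast = Δ − cΔ = (1 − c)Δ.

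These are separate routes. Already-exposed people in the sweetener arm dilute only the first comparison, and exposed controls dilute only the second. Randomisation makes f and c equal in expectation, but it does not remove either dilution.

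**Step 3: scale with 20 per arm (Section 10.2).** The number of exposed controls is an assumption; the protocol gives none.

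- 2 of 20: 1 − 2/20 = 0.90 of Δ remains
- 4 of 20: 1 − 4/20 = 0.80 of Δ remains
- 6 of 20: 1 − 6/20 = 0.70 of Δ remains

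If habitual intake produces only a fraction g of the effect, the factor becomes 1 − cg, which is a smaller loss.

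**Step 4: would the plan's own checks show it?** Section 10.4.1 compares baselines across the three groups and expects the two control time-points to be similar. Stable habitual use spread across arms passes both checks. Neither can reveal the problem.

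**The case against.** Several points on the other side are fair.

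- **Controls may not add polyols.** A reader might infer that controls are free to start the test substance. The synopsis and the German summary describe what participants take, not only what is supplied, and a control who began a polyol would depart from them. Only use already established before entry is left open.
- **Diet recording is broader than two diary weeks.** The questionnaire, the 7-day baseline diary and the account in Section 5.1 could reveal habitual use. This stands, although the sweetener entry in Section 5.1 may refer to study sticks, and recording does not prevent exposure.
- **Availability is not intake.** The study doses are 24 g of xylitol and 36 g of erythritol daily, and Section 2.3 relates them to about 24 g of table sugar a day (20% of 120 g). Presence in foods and dental products does not show that volunteers take comparable amounts.
- **Power.** A reader might turn the dilution into power. Starting from an assumed 80% at 20 per arm, 10%, 20% or 30% dilution would leave roughly 71%, 61% or 50%. No document supports those rates. Section 10.2 says no power analysis is possible, and Section 10.1 calls hypothesis testing inapplicable. Nor does it follow that a null result would be uninterpretable.
- **Tolerability.** A reader might infer that adapted users flatter tolerability. Every sweetener participant passes through an adaption week, and Sections 4.2 and 8.2.2 put the on-treatment symptom scores at weeks 3 and 7 (Section 5.1 says weekly). The argument is weak.
- **Artificial sweeteners and other studies.** Section 2.1 cites one study "demonstrating that consumption of commonly used artificial sweeteners drive the" development of glucose intolerance, and Section 2.4 says only that metabolic side-effects are probable. That supports holding such use constant, not excluding users. The criterion "Participation in another study with investigational drug within the 30 days preceding and during the present study" would not catch an earlier polyol study, but nothing shows that such volunteers are expected. Both points are secondary.
- **Unseen forms.** The pre-screening form and study folder listed in Section 15 are not shown and may ask the question. Even so, Section 6.1 is where an exclusion belongs.

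**Conclusion.** The point holds in limited form. As written, the protocol admits regular xylitol or erythritol users and lets them continue. Their baseline values are already exposed, and those in the control arm are not without treatment. Both effects run toward no difference.

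The size cannot be given. It depends on how many volunteers are habitual users and on how much of the effect their intake produces, and the protocol reports neither. The factors 1 − f and 1 − c assume full effect in habitual users and so mark the upper end of the loss for a given share. This is a cheap improvement and not a defect that invalidates the design.

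**What to change.** 1. **Section 6.1 and synopsis:** add an exclusion for regular intake of xylitol- or erythritol-containing sweeteners or products before V1. The sponsor sets the window; the documents give no basis for a particular length.
2. **Sections 7.2.1 and 7.2.2:** state that all three arms take no xylitol or erythritol from non-study sources until V3 and keep artificial-sweetener use unchanged.
3. **Sections 5.1 and 8.2.3:** name both items in the existing diary and ask about them in the weekly calls already planned.

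Cost: a protocol amendment, a question at pre-screening and a line in the call script. A few regular polyol users will be screened out. Artificial-sweetener users stay eligible, so the loss to recruitment should be small.

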6.2 Recruitment and screening

Participant recruitment will be achieved through referring physicians from the Ernährungszentrum St. Claraspital, where morbidly obese patients are seen in an outpatient clinic before bariatric surgery and are usually on a rather long waiting list before surgery. In case patients are interested in participating, they will be contacted by the principal investigator (Dr: [name]) or the study nurse ([name]) per email, phone or face-to-face and a pre-screening is carried out (key questions to find out whether a volunteer is eligible). If the volunteer meets these key criteria, a screening appointment will be made and informed consent is sent by email or mail, so that the volunteer gets the chance to read through the information material before the screening visit.

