4.2 Secondary Outcomes

- Human gut microbiota composition: Faecal samples will be taken before and after treatment and the taxonomic and functional profiles of the gut microbiota will be assessed by metagenomic shotgun sequencing.
- Metabolomics: Faecal and urine samples will be used for analysis of the metabolome using metabolomics.
- Blood lipid profile, hsCRP and hepatic enzymes: Fasting samples will be taken to measure triglyceride, total cholesterol, LDL and HDL levels, and the liver enzymes ASAT (aspartate transaminase) and ALAT (alanine transaminase). The analysis will be carried out in the hospital laboratory (St. Claraspital).
- **Inflammatory response:** As erythritol might act as a radical scavenger and reduce oxidative stress, we plan to assess inflammatory state by measuring IL-6, TNF-α, sTNFR1, sTNFR2, high sensitive CRP (hsCRP) and leucocytes.
- Intestinal permeability: Circulating markers of intestinal permeability (zonulin, LPS) will be measured.
- Gastrointestinal tolerance (bloating, diarrhoea etc.): We will assess gastrointestinal symptoms by using a validated questionnaire (Clinical rating scale for gastrointestinal symptoms: Svedlund et al.²¹). The questionnaire will be used at baseline and at the end of week 3 and 7 (self-reporting). A license agreement will be sent to AstraZeneca (ASTRAZENECA AB, 556011-7482 S-151 85 Södertälje, Sweden).
- 4.3 Intestinal Glucoseabsorption: We will assess intestinal glucose absorption by use of a validated technique: during the oral glucose tolerance test, 3g of 3-O-Methyl-Glucose (3-OMG) is ingested. 3-OMG is then measured in the plasma samples obtained at 0-30-60-90-120min. Other Outcomes of Interest

We accept that a possible confounder might be the substitution of sucrose in daily life as polyols might serve as a substitute. If sugar consumption is reduced, metabolic effects could be caused by reduced sugar exposure rather than polyol intake. We will therefore assess overall sugar consumption before and during the trial. Participants will keep a food diary. For this purpose we will use the clinical diary used by our nutritionists for preoperative assessment of bariatric patients.

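### Participants come from a pre-bariatric clinic, but eligibility leaves scheduled surgery and concurrent weight-loss treatment unaddressed, which exposes the within-arm before-after test to bias

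*Protocol*

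**What the plan says.** **Source of participants.** Protocol sections 5.1 and 6.2 recruit through the hospital's nutrition centre, where "morbidly obese patients are seen in an outpatient clinic before bariatric surgery and are usually on a rather long waiting list before surgery". Section 4.3 takes its food diary from the same setting: it is "the clinical diary used by our nutritionists for preoperative assessment of bariatric patients".

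**Eligibility (section 6.1).** The inclusion criteria are "Obese volunteers (BMI > 30kg/m2) aged 18- max. 55 years", "Otherwise healthy" and informed consent. The surgical exclusion looks backwards only: "history of gastrointestinal surgery with major changes to the gastrointestinal tract (removal of stomach, larger portions of the small bowel/colon, any bypass". The exclusions for treated metabolic conditions are "Diabetes mellitus treated by oral antidiabetics or insulin", "Arterial hypertension with antihypertensive treatment" and "Dyslipidaemia with statin therapy". Neither section 6.1 nor the synopsis mentions scheduled surgery, a current or planned weight-loss programme, a weight-lowering drug or weight stability.

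**Conduct.** The withdrawal reasons in section 6.4 do not include weight-loss treatment or surgery. Section 7.6 asks participants to report antibiotics. Section 5.2 names one dietary confounder, the replacement of sugar by the polyol.

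**Analysis.** Section 10.1 expects better glycaemic control relative to baseline. Section 10.4.1 treats each participant as his or her own control and expects the control group's two time points to agree. Section 10.4.2 tests before against after by paired t-test at P < 0.05 and compares groups by one-way ANOVA.

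**The concern.** A before-after comparison is interpretable only if the outcome would have stayed put without the sweetener. The participants are under care for obesity and await an operation for it. Weight reduction, or starting a glucose- or weight-lowering drug, between the two glucose tolerance tests would itself be expected to move glucose, insulin and C-peptide. Nothing in section 6.1 prevents this, so a paired test in a sweetener arm could credit the polyol with an improvement that came from elsewhere.

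The drug wording is also narrow. Read literally, the diabetes bullet does not cover an injected non-insulin agent, or a glucose-lowering drug taken without a diabetes diagnosis, and weight-loss drugs are not named. The bullet also sits awkwardly with the intended cohort. Sections 2.1 and 10.1 describe non-diabetic patients, and the German summary requires that there be no diabetes at all, whereas section 6.1 excludes diabetes only when it is treated in certain ways.

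Being otherwise healthy does not settle the matter. Section 2.6 expects dyslipidaemia and impaired glucose tolerance in virtually all morbidly obese patients, and the study enrols such patients.

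**Working it through.** **Inputs from the protocol.** n = 20 per arm (section 10.2); paired t-test, P < 0.05 (section 10.4.2), taken as two-sided because sidedness is not stated. The group size was chosen on practical grounds and no SD is given, so there is no power figure to reproduce.

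**Assumptions, not in the protocol.** A share q of an arm is affected. Each affected person's OGTT measure shifts by s, in units of the SD of within-person change among unaffected participants. The sweetener has no effect.

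**Formulas.**
- Mean change in the arm = q·s
- Variance factor = 1 + q(1 − q)s²
- Noncentrality λ = q·s·√20 / √(1 + q(1 − q)s²)
- False-positive rate = P(|T| > 2.093), with T noncentral t on 19 df

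**Example**, q = 0.3 and s = 1: mean 0.30; variance 1 + 0.3 × 0.7 = 1.21, so SD 1.10; λ = (0.30/1.10) × 4.472 = 1.220; rate 21.2%. If everyone drifts by 0.30 instead, there is no extra variance: λ = 0.30 × 4.472 = 1.342; rate 24.7%.

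**Paired test, one sweetener arm of 20, no sweetener effect:**

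| Scenario | q = 20% | q = 30% | q = 50% |
|---|---|---|---|
| s = 1 SD | 12.4% | 21.2% | 47.6% |
| Same mean drift (0.2 / 0.3 / 0.5 SD) in everyone | 13.6% | 24.7% | 56.5% |
| s = 0.5 SD | 7.0% | 9.5% | 17.8% |
| s = 0.25 SD | 5.5% | 6.2% | 8.2% |

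The result depends heavily on s, which the protocol gives no means of fixing.

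**Randomised comparison, 20 against 20.** With q and s equal in expectation across arms, simulation at s = 1 (t-test on change, no sweetener effect) rejects in about 5% of trials for q = 20, 30 and 50%. The cost is variance, which rises by 16%, 21% and 25%. Chance differences between arms in the number affected (at q = 30%, SD √(2 × 0.3 × 0.7/20) = 0.145, about 14 percentage points) are already contained in that variance and are not a further harm.

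**Condition on the 5%.** The control arm is open (section 5.2.2). If mean drift differed between arms by 0.2, 0.3 or 0.5 SD, the two-sample test would reject in 9.5%, 15.2% or 33.8% of trials. The protocol gives no evidence that it would differ.

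**The case against.** The strongest reply is that the premise is inferred. No section says that waiting-list patients are dieting, losing weight or starting drugs, and a diary used for preoperative assessment is not treatment. This stands, and it is why the figures are a range under assumptions and not an estimate.

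A reader might go further and infer that weight loss could produce the trial's OGTT result as a whole. The protocol does not support that. All three arms are randomised from the same source, and the untreated arm is there to show whether findings are stable over 7 weeks. Drift common to the clinic would appear in the controls too, and the randomised test keeps its error rate.

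A reader might also infer that operations before the final visit will remove primary outcomes. The waiting list is described as long, which makes this unlikely within about 8 weeks, and section 10.4.1 replaces drop-outs. It is a minor loose end.

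It can fairly be said that a paired test is open to any drift, such as regression to the mean, and that eligibility rules alone would not cure it. That is right, and the fix therefore also addresses which comparison carries the conclusion.

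Some mitigation exists. Weight is measured at screening and the final visit, food diaries are kept, and concomitant medication is source data (section 11.1.2). These allow description afterwards, but the protocol attaches no rule to them. Reporting weight by arm is ordinary analysis-plan content, and its absence here is not itself a fault.

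Lastly, this is an exploratory pilot. Section 10.1 says hypothesis testing does not apply, yet section 10.4.2 sets a significance threshold for the paired test, so a significant result would still be read as evidence.

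**Conclusion.** The gap is real but limited. Section 6.1 does not deal with scheduled surgery or concurrent weight-loss treatment in a population drawn from a pre-bariatric clinic, and its diabetes wording does not secure the non-diabetic cohort described elsewhere. The exposure falls on the within-arm paired test. One arm of 20 would give a false positive in roughly 12–14%, 21–25% or 48–57% of trials at mean drifts of 0.2, 0.3 or 0.5 SD, and in 5.5–18% if 20–50% of participants shift by 0.25–0.5 SD each. The prevalence and the size of shift are assumptions. The randomised comparison stays near 5% provided drift is equal across arms, and loses only some precision. This is a worthwhile and inexpensive improvement, not a defect that undermines the trial.

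**What to change.** 1. Add to section 6.1, and ask at the pre-screening already described in section 6.2, that no bariatric surgery or preoperative diet is scheduled before the final visit, and that no weight-reduction programme or weight- or glucose-lowering drug is in use or planned before then. Whether to add a weight-stability limit, and at what value, is for the sponsor.
2. Reconcile the diabetes bullet in section 6.1 with the non-diabetic cohort of sections 2.1 and 10.1 and with the German summary.
3. Record any such treatment started during the study.
4. Report weight change from screening to the final visit by arm beside the OGTT result. Use it as description: weight change caused by the sweetener would lie on the causal path.
5. State in sections 10.1 and 10.4.2 that any conclusion of benefit rests on the randomised comparison with control, with the within-arm tests as description.

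The cost is a protocol amendment and a few pre-screening questions. No new procedure is needed. Some waiting-list candidates would be deferred, which may slow recruitment at a single centre, and section 1.14 lists insufficient recruitment as a ground for stopping early.
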